### Osimertinib (AZD9291)

#### **Dose Adjustments for Osimertinib (AZD9291):**

Dose Level	Osimertinib (AZD9291) Dose (QD)
Starting Dose	80 mg
Dose Reduction	40 mg

All patients in the phase 2 study will commence treatment with Osimertinib (AZD9291) at 80 mg daily. If a patient experiences a persistent drug-related grade 2 event or any CTCAE grade 3 or higher and/or unacceptable toxicity (any grade), where the clinician considers the event of concern to be specifically associated with Osimertinib (AZD9291) (and not attributable to the disease or disease-related processes for which patient is being treated), dosing will be interrupted, and supportive therapy administered as required in accordance with local practice/guidelines. If a toxicity resolves or reverts to  $\leq$ CTCAE grade 2 within 3 weeks of onset, treatment with Osimertinib (AZD9291) may be restarted at the same dose (80 mg) or a lower dose (40 mg) using the rules indicated in the above table for dose modifications and with discussion and agreement with the Sponsor Study Team Physician as needed. There will be no individual modifications to dosing schedule in response to toxicity, only potential dose reduction or dose interruption. If the toxicity does not resolve to  $\leq$ CTCAE grade 2 after 3 weeks, then the patient should be withdrawn from the study and observed until resolution of the toxicity.

Dose adjustment for AEs should be in accordance with the following table:

Dose Adjustment Information for Adverse Reactions		
Target Organ	Adverse Reaction	Dose Modification

Pulmonary	ILD/Pneumonitis	Permanently discontinue Osimertinib (AZD9291)
Cardiac	QTc interval greater than 500 msec on at least 2 separate ECGs	Withhold Osimertinib (AZD9291) until QTc interval is less than 481 msec or recovery to baseline if baseline QTc is greater than or equal to 481 msec, then restart at a reduced dose (40 mg) or at 80 mg (at the discretion of the investigator, to allow for situations where
		causality in relation to osimertinib may be difficult to determine).
	QTc interval prolongation with signs/symptoms of serious arrhythmia	Permanently discontinue Osimertinib (AZD9291)
Other	Grade 3 or higher adverse reaction	Withhold Osimertinib (AZD9291) for up to 3 weeks
	If grade 3 or higher adverse reaction improves to grade 0-2 after withholding of Osimertinib (AZD9291) for up to 3 weeks	Osimertinib (AZD9291) may be restarted at the same dose (80 mg) or a lower dose (40 mg)
	Grade 3 or higher adverse reaction that does not improve to grade 0-2 after withholding for up to 3 weeks	Permanently discontinue Osimertinib (AZD9291)

On resolution of toxicity within 3 weeks:

- If an AE subsequently requires dose interruption, Osimertinib (AZD9291) may restart at the same dose or the reduced dose, on resolution/improvement of the AE at the discretion of the Investigator.

Patients experiencing any of the following AEs will not be permitted to restart study treatment:

- Interstitial Lung Disease (ILD)
- QTc interval prolongation with signs/symptoms of serious arrhythmia

NCI Protocol #: 10216

Version Date: 09/17/2024

There is no dose reduction allowed below 40 mg. If a patient experiences toxicity such that 40 mg is no longer considered tolerable, the patient should discontinue study treatment.

It is recommended that all patients follow a program of sun protective measures while receiving study drug and for 3 to 4 weeks after discontinuing study drug.

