## **7 DOSING DELAYS/DOSE MODIFICATIONS.**

### **Telaglenastat (CB-839) HCl**

Based on available data, AEs that are most likely to be observed with Telaglenastat (CB-839) HCl treatment include fatigue, GI events (nausea, vomiting, anorexia), photophobia, and elevated LFTs. Careful application of the dose-escalating rules and close observation of the subjects should minimize the potential risk of dosing with Telaglenastat (CB-839) HCl. The study personnel must be able to recognize and diagnose these potential AEs and initiate prompt intervention. In general, grade 1 events should be managed with appropriate supportive care, dosing can be interrupted for persistent drug-related grade 2 events, and the dose should be reduced for most Telaglenastat (CB-839) HCl-related grade 3/4 toxicities. In particular, regular monitoring of LFTs is recommended. Grade  $>2$  elevations in ALT or total bilirubin should lead to an interruption of study drug and grade  $\geq 3$  events should lead to dose reduction upon restarting Telaglenastat (CB-839) HCl.

Blood Bilirubin Increase	Management/Next Dose for Telaglenastat (CB-839) HCl	Management/Next Dose for Osimertinib (AZD9291)
Grade 1	No change in dose.	No change in dose
Grade 2	Hold until $\leq$ grade 1. Resume at same dose level.	Hold until $\leq$ grade 1. Resume at same dose level.
Grade 3	Hold* until $\leq$ grade 1. Resume at one dose level lower, if indicated. **	Hold* until $\leq$ grade 1. Resume at one dose level lower, if indicated. **
Grade 4	Hold* until $\leq$ grade 1. Resume at one dose level lower, if indicated. **	Hold* until $\leq$ grade 1. Resume at one dose level lower, if indicated. **

\*Patients requiring a delay of  $>2$  weeks should go off protocol therapy.

\*\*Patients requiring  $> 2$  dose reductions of Telaglenastat (CB-839) HCl or  $> 1$  dose reduction in Osimertinib (AZD9291) must go off protocol therapy.

Alanine Aminotransferase Increased	Management/Next Dose for Telaglenastat (CB-839) HCl	Management/Next Dose for Osimertinib (AZD9291)
Grade 1	No change in dose.	No change in dose
Grade 2	Hold until $\leq$ grade 1. Resume at same dose level.	Hold until $\leq$ grade 1. Resume at same dose level.
Grade 3	Hold* until $\leq$ grade 1. Resume at one dose level lower, if indicated. **	Hold* until $\leq$ grade 1. Resume at one dose level lower, if indicated. **

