Grade 4	Hold* until $\leq$ grade 1. Resume at one dose level lower, if indicated. **	Hold* until $\leq$ grade 1. Resume at one dose level lower, if indicated. **

\*Patients requiring a delay of  $>2$  weeks should go off protocol therapy.

Alanine Aminotransferase Increased	Management/Next Dose for Telaglenastat (CB-839) HCl	Management/Next Dose for Osimertinib (AZD9291)
** Patients requiring $> 2$ dose reductions of Telaglenastat (CB-839) HCl or $> 1$ dose reduction in Osimertinib (AZD9291) must go off protocol therapy.		

Other AEs	Management/Next Dose for Telaglenastat (CB-839) HCl	Management/Next Dose for Osimertinib (AZD9291)***
Grade 1	No change in dose. Administer standard supportive care.	No change in dose
Grade 2	For persistent grade 2 toxicity****: Hold until $\leq$ grade 1. Resume at same dose level.	For persistent grade 2 toxicity****: Hold until $\leq$ grade 1. Resume at same dose level.
Grade 3	Reduce dose by one level if event is related to Telaglenastat (CB-839) HCl.*	Hold* until $\leq$ grade 1. Resume at one dose level lower, if indicated. **

Grade 4	Reduce dose by one level if event is related to Telaglenastat (CB-839) HCl.*	Hold* until $\leq$ grade 1. Resume at one dose level lower, if indicated.**
---------	--	---

\*Patients requiring a delay of  $>2$  weeks should go off protocol therapy.

\*\* Patients requiring  $> 2$  dose reductions of Telaglenastat (CB-839) HCl or  $> 1$  dose reduction in Osimertinib (AZD9291) must go off protocol therapy.

\*\*\* Osimertinib (AZD9291) must be permanently discontinued for ILD/pneumonitis or QTc interval prolongation with signs/symptoms of serious arrhythmia

\*\*\*\* Persistent grade 2 toxicities include those that do not resolve within 7 days despite optimal

supportive care or result in treatment delay  $> 14$  days

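### Section 7 gives two incompatible osimertinib hold-and-restart rules for grade 3 or higher events that have no event-specific rule, and does not say which governs

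*Combined protocol and SAP*

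**What the plan says.** Section 7 covers osimertinib holds in two places.

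**The adverse event tables (bilirubin, ALT, Other AEs).** They sit under a telaglenastat heading, but each has a separate osimertinib column. For grade 3 and grade 4, osimertinib is held until grade 1 or lower, then "Resume at one dose level lower, if indicated". The footnote attached to the hold says that patients whose delay exceeds 2 "weeks should go off protocol therapy". The grade 2 row of the Other AEs table reads "For persistent grade 2 toxicity", with a hold to grade 1 or lower.

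**The osimertinib subsection (a narrative, then a dose adjustment table).** The narrative opens with "All patients in the phase 2 study will commence treatment with Osimertinib (AZD9291) at 80 mg daily". It applies to events "where the clinician considers the event of concern to be specifically associated with Osimertinib (AZD9291)". It allows restart at 80 mg or 40 mg once the toxicity is at most "grade 2 within 3 weeks of onset", with sponsor physician agreement as needed. The table says "Withhold Osimertinib (AZD9291) for up to 3 weeks" for other grade 3 or higher reactions. The restart row begins "If grade 3 or higher adverse reaction improves to grade 0-2 after withholding of Osimertinib (AZD9291) for up to 3 weeks", and restart at either dose may follow. Otherwise osimertinib is permanently discontinued.

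Separate text in Section 7 covers ILD/pneumonitis, QTc prolongation, SJS/TEN, aplastic anemia and diarrhea.

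**The concern.** The recovery grade and the maximum hold both differ for the same drug and the same event. A site working from the osimertinib subsection may restart a patient whom a site working from the adverse event tables would take off protocol therapy. Sponsor physician agreement, sought only as needed, is a partial check.

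At stake are consistent handling of osimertinib toxicity and the meaning of the descriptive data on discontinuation, dose changes and exposure, in a trial whose primary objective is safety and tolerability. The stopping action matters for the data too: Section 6.4 has the case report form record reasons for ending protocol therapy and reasons for leaving the study as separate items. The point is still live after accrual has closed, because Section 6.1 lets patients stay on osimertinib alone after telaglenastat supply ends on 2/28/25, until they meet another off-therapy criterion. The delay limit is one such criterion.

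**Working it through.** The plan states no figure to reproduce. The check sets the two rules side by side.

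**Inputs**, both in days of osimertinib hold: T1 = time to grade 1 or lower; T2 = time to grade 2 or lower, so T2 ≤ T1.

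- Adverse event tables: resume at T1; off protocol therapy if T1 > 14.
- Dose adjustment table: restart permitted from T2 if T2 ≤ 21; otherwise discontinue.

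**Comparison**

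| Recovery pattern | Adverse event tables | Dose adjustment table |
|---|---|---|
| T1 ≤ 14 | resume at T1 | may restart from T2, which is T1 − T2 days earlier if grade 2 comes first |
| T1 > 14 and T2 ≤ 21 | off protocol therapy | may restart from T2 |
| T2 > 21 | off protocol therapy (already past 14 days) | permanently discontinue osimertinib |

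The middle row is the contradiction. The first row is a difference in timing only. In the third row both stop osimertinib, with different stated actions.

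**Examples**

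- T2 = 5, T1 = 12: restart permitted from day 5 or from day 12, a gap of 12 − 5 = 7 days.
- T2 = 5, T1 = 16: off protocol therapy under the first rule, since 16 > 14; restart permitted from day 5 under the second.
- T2 = 16, and so T1 ≥ 16: off protocol therapy under the first; restart permitted on day 16 under the second, since 16 ≤ 21.

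**Does any wording settle precedence?**

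- *Heading.* The telaglenastat heading does not exclude osimertinib, because the tables have an osimertinib column and a footnote specific to that drug.
- *Pointer upward.* The narrative sends the reader to a table above it. That could be the 80/40 mg table directly above or the adverse event tables. The same sentence sets grade 2 and 3 weeks, so it does not import grade 1 and 2 weeks.
- *Pointer downward.* The narrative then directs dose adjustment to the table below it, but does not disapply the earlier tables.
- *Cohort.* The narrative's opening, and the Section 6.1 remark on reducing osimertinib for phase 2 patients, suggest that the narrative is limited to the expansion cohort. The adverse event tables and the dose adjustment table carry no cohort limit, so the conflict remains at least there.

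**Lesser differences to settle at the same time**

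- *Clock.* The 3 weeks run from onset in the narrative and from withholding in the table. With d days from onset to hold, the two disagree for 21 − d < T2 ≤ 21. The documents do not give d. Over an assumed range of 0 to 7 days, the disagreement runs from none (d = 0) to hold days 15-21 (d = 7).
- *Stopping action.* The narrative withdraws the patient from the study, the dose adjustment table discontinues osimertinib, and the adverse event tables end protocol therapy.
- *Persistent grade 2.* The Other AEs table holds to grade 1 or lower. Read literally, the narrative's restart condition is already met when the hold begins.
- *QTc above 500 msec.* The QTc paragraph names only a reduced restart dose; the dose adjustment table also allows 80 mg.
- *Diarrhea.* The diarrhea table has its own grade 3/4 rule, but its closing text refers back to dose adjustment guidelines above without saying which.

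**The case against.** The best case on the other side accepts the mismatch and disputes its reach.

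- *Scope.* Diarrhea, SJS/TEN and aplastic anemia have their own text, as do ILD/pneumonitis and QTc events. This stands, and the point is limited accordingly.
- *Permissive wording.* The osimertinib subsection permits restart and does not require it, so a cautious site could satisfy both rules. True for that site, but nothing says the 2-week limit still binds, and the subsection sets its own later stopping point.
- *Lesser differences.* Withdrawing a patient and discontinuing a drug can both be done; onset and hold may nearly coincide, since the narrative calls for interruption; and the grade 2 wording can be read as requiring resolution. These are fair replies, so those items are wording to tidy and not further contradictions.
- *Evaluability.* A reader might infer that the choice of rule decides whether a patient meets the Section 6.2 condition of 75% of scheduled treatment days. The documents do not support this. Section 6.2 does not define how days with only osimertinib on hold are counted. For grade 3/4 Other AEs the telaglenastat column says to reduce if related and does not say to hold, so telaglenastat may be taken on those days. Stopping for treatment-related toxicity does not make a patient non-evaluable under the discontinuation rule in Sections 6.2 and 9.1. The toxicity summaries in Sections 9.1 and 9.4 require only one dose.
- *Consequences.* No affected patient is shown. This stands, and is why the report should first check the records.

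**Conclusion.** The contradiction is in the text. For grade 3 or higher osimertinib-attributed events without an event-specific rule, one rule takes the patient off protocol therapy and the other permits restart whenever T1 > 14 and T2 ≤ 21. When T1 ≤ 14, permitted restart can differ by T1 − T2 days. This rests on reading the osimertinib columns as binding and on no unseen precedence statement.

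The finding is limited to that. The DLT definition, the 3+3 rule and the rule stopping the expansion at 5 DLTs in 10 patients do not change. The number of patients affected cannot be computed. A reader might infer that patients were managed inconsistently or harmed; the documents give no data on holds and do not show it. The correction is worth making, but it does not put a primary decision rule in doubt. Because accrual is closed, it helps only patients still on treatment and the accuracy of the study report.

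**What to change.** The sponsor should reconcile the osimertinib columns of the adverse event tables with the osimertinib narrative and dose adjustment table, and with the QTc and diarrhea text, or state which passage governs by event type and cohort. The wording should settle the maximum hold, the event that starts its clock, the recovery grade (including for persistent grade 2), the restart dose and the stopping action. Which rule is right is for the sponsor's clinicians; this review takes no view. Sites with patients still on treatment should be told.

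For the study report, the study team should check recorded osimertinib holds and discontinuations for any that fell where the rules diverge. Section 6.4 already collects reasons and dates for stopping, and the Appendix G diary records daily intake. Any such cases should be disclosed.

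The cost is protocol wording, a memo to sites, a short records check and, if cases are found, a sentence in the report.

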### **Interstitial Lung Disease (ILD)/Pneumonitis-like toxicity:**

If new or worsening pulmonary symptoms (e.g., dyspnea) or radiological abnormality suggestive of interstitial lung disease is observed, an interruption in study treatment dosing is recommended, and the AstraZeneca study team should be informed. It is strongly recommended to perform a full diagnostic workup, to exclude alternative causes such as lymphangitic carcinomatosis,

infection, allergy, cardiogenic edema or pulmonary hemorrhage. The results of full diagnostic workup (including high resolution computed tomography (HRCT), blood and sputum culture, hematological parameters) will be captured by eCRF. In the presence of confirmatory HRCT scans where other causes of respiratory symptoms have been excluded, a diagnosis of interstitial lung disease should be considered and study treatment permanently discontinued

### **Management of Keratitis**

Keratitis was reported in 0.7% (n=6) of the 833 patients treated with Osimertinib (AZD9291) in the AURA studies. Patients presenting with signs and symptoms suggestive of keratitis such as acute or worsening: eye inflammation, lacrimation, light sensitivity, blurred vision, eye pain, and/or red eye should be referred promptly to an ophthalmology specialist.

### **Management of QTC Prolongation**

For QTc interval greater than 500 msec on at least 2 separate ECGs, withhold Osimertinib (AZD9291) until QTc interval is less than 481 msec, or until recovery to baseline if baseline QTc is greater than or equal to 481 msec. Osimertinib (AZD9291) can then be restarted at a reduced dose. If the toxicity does not resolve to grade  $\leq 2$  within 21 days, the patient will be permanently withdrawn from study treatment.

For QTc interval prolongation with signs/symptoms of serious arrhythmia, Osimertinib (AZD9291) must be permanently discontinued.

### **Changes in Cardiac Contractility**

An Echocardiogram or MUGA scan to assess LVEF will be performed at screening (prior to first dose of Osimertinib (AZD9291)) and at end of treatment. Per the FDA label, echocardiogram is indicated at baseline and during treatment for patients with cardiac risk factors, or if clinically indicated.

The modality of the cardiac function assessments must be consistent within a patient i.e. if echocardiogram is used for the screening assessment then echocardiogram should also be used for subsequent scans. The patients should also be examined using the same machine and operator whenever possible, and quantitative measurements should be taken. A 28-day follow-up assessment will be required if an on-treatment assessment was abnormal at the time of discontinuation of study therapy, to confirm reversibility of the abnormality.

### **Erythema Multiforme, and Stevens-Johnson syndrome and Toxic epidermal necrolysis**

Case reports of Erythema multiforme (EM) and toxic epidermal necrolysis have been uncommonly reported, and Stevens-Johnson syndrome (SJS) have been uncommonly and rarely reported, respectively, in association with osimertinib treatment. Before initiating treatment, patients should be advised of signs and symptoms of EM, and SJS and TEN. If signs and symptoms suggestive of EM develop, close patient monitoring and drug interruption or discontinuation of osimertinib should be considered. If signs and symptoms suggestive of SJS appear, osimertinib should be interrupted. Osimertinib should be discontinued immediately if SJS or TEN is diagnosed.

### **Aplastic Anemia**

Rare reports of aplastic anemia have been reported in association with osimertinib treatment. Some cases had a fatal outcome. Before initiating treatment, patients should be advised of signs and symptoms of aplastic anemia including but not limited to persistent fever, bruising, bleeding, and/or pallor. If signs and symptoms suggestive of aplastic anemia develop, close patient monitoring and drug interruption or discontinuation of osimertinib should be considered. Osimertinib should be discontinued in patients with confirmed aplastic anemia.

## Dose Modifications and Supportive Care for Diarrhea

Severity (CTCAE v5.0 Grading)	Description	Intervention concerning Osimertinib (AZD9291) treatment	Specific intervention
Mild (Grade 1)	Increase of <4 stools per day over baseline; mild increase in ostomy output compared with baseline	Continue same dose	Stop laxatives and advise patient to drink at least 8-10 glasses of water of clear fluids per day. Consider adding loperamide. 4 mg (2 tablets) of loperamide to be taken immediately, followed by 2 mg (1 tablet) after each loose stool until bowel movements cease for 12 hours.
Moderate (Grade 2)	Increase of 4-6 stools per day over baseline; IV fluids indicated <24 hours; moderate increase in ostomy output compared with baseline; not interfering with ADL	Continue same dose with medical management unless investigator determines clinically significant and persists >72 hours.  Then interrupt Osimertinib (AZD9291) until grade $\leq 1$ and consider a dose reduction.	Start loperamide if patient not already taking per dosing above. 4 mg (2 tablets) of loperamide to be taken immediately, followed by 2 mg (1 tablet) after each loose stool until bowel movements cease for 12 hours. If already on loperamide, consider adding diphenoxylate/atropine (lomotil) and/or tincture of opium.

Severe (Grade 3)	Increase of $\geq 7$ stools per day over baseline; incontinence; IV fluids $>24$ hours; hospitalization; severe increase in ostomy output compared with baseline; interfering with ADL	Dose interruption until recovered to $\leq$ grade 1 followed by dose reduction.	See grade 2; plus: Consider an infectious process. Aggressive IV fluid replacement; consider hospitalization to monitor progress.
Life threatening (Grade 4)	Life-threatening consequences (e.g., haemodynamic collapse)	Dose interruption until recovered to $\leq$ grade 1 followed by dose reduction	See grade 3

Appropriate management of diarrhea, including dose adjustments for AEs of diarrhea that are of CTCAE grade  $\geq 3$  or that are clinically significant and/or intolerable and considered by the Investigator to be causally related to Osimertinib (AZD9291), should be undertaken as per standard practice and guidelines for dose adjustments above. Changes in CTCAE grade of diarrhea will be captured in the AE eCRF.

Nausea, vomiting, or both may be controlled with anti-emetic therapy per local practice..

## 8 PHARMACEUTICAL INFORMATION

A list of the AEs and potential risks associated with the investigational agents administered in this study can be found in Section 10.1.

### 8.1 CTEP IND Agents

#### 8.1.1 Telaglenastat (CB-839) HCl (NSC 795998)

**Chemical Name:** N-[5-[4-[6-[[2-[3-(trifluoromethoxy)phenyl]acetyl]amino]-3-pyridazinyl]butyl]-1,3,4-thiadiazol-2-yl]-2-pyridineacetamide

**Classification:** Glutaminase Inhibitor

**Molecular Formula:** C26H24F3N7O3S      **M.W.:** 571.57

**Mode of Action:** Telaglenastat (CB-839) HCl is a potent and selective reversible inhibitor of glutaminase activity. It is an allosteric and noncompetitive inhibitor of both GAC (“glutaminase C”) and KGA (“kidney glutaminase”) isoforms of glutaminase (GLS), but does not inhibit glutaminase-2.

**How Supplied:** Telaglenastat (CB-839) HCl is supplied as 200 mg white to off-white oval coated tablets. Each tablet contains 200 mg Telaglenastat (CB-839) HCl salt which is equivalent to 188 mg of CB-839 free base. Tablet excipients include microcrystalline cellulose, lactose monohydrate, sodium starch glycolate, magnesium stearate, and Opadry II White (coating). The approximate dimensions (L x W x H) are 14.5 mm x 6.9 mm x 6.0 mm (0.57" x 0.273" x 0.236"). Each 50-count bottle is sealed with a tamper-evident seal and a child-proof cap. Tablets can be transferred to another bottle per institutional procedure prior to dispensing.

In late 2021 PMB will transition to a new formulation of telaglenastat (CB-839) HCl. This new telaglenastat (CB-839) HCl formulation is supplied as 200 mg purple, oval, coated tablets embossed with the letters "TEL" on one side of the tablet. Each tablet contains 200 mg CB-839 HCl salt which is equivalent to 188 mg of CB-839 free base. Tablet excipients include microcrystalline cellulose, lactose monohydrate, sodium starch glycolate, magnesium stearate, and Opadry® II 85F90035 Purple (coating). This color is free from potentially allergenic dyes and is an approved color for US and EU markets. The approximate dimensions (L x W x H) are 14.5 mm x 6.9 mm x 6.0 mm (0.57" x 0.273" x 0.236").

Each 240-count bottle is sealed with a tamper-evident seal and a child-proof cap. The packaging consists of white opaque high-density polyethylene (HDPE) plastic bottles closed with a child resistant cap (CRC) and sealed with a tamper-evident induction seal. No rayon in bottle. Tablets can be transferred to another bottle per institutional procedure prior to dispensing.

**Storage:** Store at room temperature (20°C-25°C). Excursions +/- 5°C are permitted.

If a storage temperature excursion is identified, promptly return Telaglenastat (CB-839) HCl to (20°C-25°C) and quarantine the supplies. Provide a detailed report of the excursion (including documentation of temperature monitoring and duration of the excursion) to for determination of suitability.

**Stability:** Stability studies are ongoing.

**Route of Administration:** PO, approximately 12 hours apart, with food. Administer the first dose immediately after breakfast, the second dose approximately 12 hours later. Doses should be taken at approximately the same times each day. Missed doses may be taken if it is not more than three hours past the scheduled administration time for the missed dose. Vomited doses should not be made up.

**Metabolism:** In *in vitro* studies, Telaglenastat (CB-839) HCl is metabolized by amide hydrolysis and to a lesser extent, P450-mediated hydroxylation.

**Potential Drug Interactions:** In *in vitro* data, Telaglenastat (CB-839) HCl is a weak inhibitor of CYP2C9; therefore, concomitant medications that are metabolized by CYP2C9 should either be given with caution (including closely monitoring for signs of toxicity or altered efficacy) or substituted with a non-CYP2C9 substrate. Telaglenastat (CB-839) HCl is not an inhibitor of CYP1A2, CYP2B6, CYP2C8, CYP2C19, CYP2D6, and CYP3A4 nor

an inducer of CYP1A2, CYP2B6, and CYP3A4.

Telaglenastat (CB-839) HCl requires low pH conditions for optimal solubilization. Concomitant use of PPIs should be avoided due to significantly reduced exposure to Telaglenastat (CB-839) HCl. Patients may be switched to shorter acting agents such as histamine H2 receptor antagonists (H2RA) and as-needed antacid buffering agents (e.g. calcium carbonate, magnesium hydroxide and aluminum hydroxide) since, based on limited clinical data, they do not appear to result in a significant reduction of Telaglenastat (CB-839) HCl exposure. It is recommended that Telaglenastat (CB-839) HCl be dosed at least 2 hours before and at least 10 hours after treatment with H2RA therapy, and at least 2 hours before or at least 2 hours after other antacid therapy.

**Patient Care Implications:** Women of child-bearing potential must have a negative pregnancy test prior to starting Telaglenastat (CB-839) HCl and use two forms of effective birth control while receiving Telaglenastat (CB-839) HCl.

